5.2. Product Accountability

The pharmacy will track use of the medication. Patients will return their bottles of medication every 4 weeks.

5.3. Treatment Compliance

This will be assessed by discussion with the patient and with pill counts in the returned bottles. Furthermore we would carefully review the diet and, in particular, try to ensure that the pills are taken correctly ie on a very empty stomach.

5.4. Concomitant Medications and Non-Drug Therapies

Concomitant ITP medications will be tracked. None can be used in the first 4 weeks of the study. Patients receiving them will be taken off study. The same is true for non-drug therapies of ITP.

5.4.1. Permitted Medications and Non-Drug Therapies

Stable doses of oral corticosteroids are allowed. No other “ITP” therapy is allowed in the study except for 3-4 weekly IVIG at doses of 300-500 mg/kg. Medication doses cannot be changed during the first 4 weeks of therapy.

5.4.2. Prohibited Medications and Non-Drug Therapies

All other ITP therapies, whether drug or non-drug, are prohibited during the first 4 weeks of therapy. Splenectomy is allowed at any time during the study however, if effective, it will end the study participation (treatment) for that subject.

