6. STUDY ASSESSMENTS AND PROCEDURES

6.1. Critical Baseline Assessments

Complete Blood Counts (CBCs)

CBCs, including platelet counts and peripheral blood smears, will be monitored prior to initiation, throughout, and following discontinuation of therapy with PROMACTA. Prior to the initiation of PROMACTA, the peripheral blood differential will be examined to establish the extent of red and white blood cell abnormalities. CBCs, including platelet counts and peripheral blood smears, will be obtained weekly during the dose adjustment phase of therapy with PROMACTA and then monthly following establishment of a stable dose of PROMACTA. CBCs, including platelet counts will be obtained weekly to biweekly for at least 4 weeks following discontinuation of PROMACTA.

Liver tests

Serum liver tests (ALT, AST, and bilirubin) will be monitored prior to initiation of PROMACTA, every 2 weeks during the dose adjustment phase and monthly following establishment of a stable dose. If bilirubin is elevated, fractionation will be performed. If abnormal levels are detected, the tests will be repeated within 3 to 5 days. If the abnormalities are confirmed, serum liver tests will be monitored weekly until the abnormality(ies) resolve, stabilize, or return to baseline levels. PROMACTA will be discontinued based on the stopping rules outlined in section 6.3.1

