6.4.3. Disease-Related Events and/or Disease-Related Outcomes Not Qualifying as SAEs

During the assessment period, thrombocytopenia that results in administration of rescue treatment does not qualify as an AE or SAE. Also during this assessment period, hospital admissions that are attributable to such treatment failures or related therapy also do not qualify as AEs or SAEs. Hemorrhagic complications of thrombocytopenia not otherwise meeting regulatory serious criteria will be reported as AEs.

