8.2. Study Design Considerations

Limited therapies exist to treat thrombocytopenia in WAS/XLT. IV gammaglobulin and corticosteroids, mainstays in ITP, are ineffective in WAS/XLT. Platelet transfusions only last for hours. The two treatments that affect the platelets in a more lasting manner are splenectomy and human stem cell transplantation (HSCT). Splenectomy successfully increases the platelet count in most patients but is associated with an increased risk of overwhelming post splenectomy sepsis (OPSS) due to the primary immune dysfunction seen in WAS/XLT. Human Stem Cell Transplantation (HSCT) is effective but has significant morbidity and mortality. Furthermore it is ideally postponed until after 24 months of age to allow TBI, which is too long to wait for affected infants with severe thrombocytopenia in view of the high risk of ICH. It is clearly necessary to establish improved therapy for thrombocytopenia in these children.

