8.3. Data Analysis Considerations

Data from all subjects who receive eltrombopag will be summarized. Results will be summarized by visit. All displays should include the number of subjects with available data at that visit.

Study endpoints include bleeding score, platelet count, platelet function, megakaryopoiesis and platelet formation.

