8.3.1.1. Efficacy Analyses

Primary endpoint will be increasing platelet counts in WAS/XLT patients to above 50,000/ul. The generalizability of the data will depend upon including both WAS and XLT patients but no specific distribution of patients within these 2 groups is pre-specified. The proportion of patients showing this increase will be summarized with 95% confidence intervals. The proportion of patients maintaining this increase will be summarized for time points of interest.

Correlations will be evaluated graphically. In addition, Spearman rank correlation coefficients may be used to evaluate the association of platelet count and bleeding score, at each visit.

Any within-subject analyses may be based on Wilcoxon signed rank tests.

Secondary endpoints will involve reduction of bleeding in treated patients within 12 weeks, and to specifically examine the reduction in bleeding in those with platelet counts > 100,000/ul and also > 50,000/ul.

We anticipate that platelet function will improve as the platelet count increases but not normalize.

Therefore efficacy will depend on platelet counts, immature platelet fraction, platelet function by flow cytometry, and the bleeding score. Since the dose required may vary from patient to patient and may only be changed every 2 weeks, a platelet count > 50,000/ul at any time within the first 12 weeks will be considered a response. Similarly, secondary endpoints involving reduction in bleeding and improvement in platelet function will also be explored within a 4 to 12 week window for assessment.

Toxicity will depend upon adverse events, abnormal liver tests, and other abnormal findings.

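### As written, a platelet rise caused by splenectomy in the first 12 weeks can be scored as a response to eltrombopag

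*Combined protocol and SAP*

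**What the plan says.** The primary endpoint in section 8.3.1.1 is a platelet count above 50,000/ul, reported as a proportion of patients with a 95% confidence interval. The operative rule is that "a platelet count > 50,000/ul at any time within the first 12 weeks will be considered a response". It requires no confirmation, does not require the patient to be on eltrombopag when the count is taken, and sets no condition on other interventions. Section 8.3 adds that "Data from all subjects who receive eltrombopag will be summarized" and gives no rule for setting counts aside.

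On splenectomy, section 5.4.2 says: "Splenectomy is allowed at any time during the study however, if effective, it will end the study participation (treatment) for that subject". Section 8.2 describes its expected effect on the endpoint: "Splenectomy successfully increases the platelet count in most patients".

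On count timing, section 6.1 says counts "will be obtained weekly during the dose adjustment phase of therapy with PROMACTA", and after the drug is stopped: "CBCs, including platelet counts will be obtained weekly to biweekly for at least 4 weeks following discontinuation of PROMACTA".

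Section 3.1 plans 15 treated patients with no placebo, each compared descriptively with their own pre-treatment state.

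**The concern.** The plan permits, inside the primary assessment window, an operation that it expects to move the primary endpoint, and it does not say how counts after that operation are scored. One count is enough for a response. A patient with no drug effect who has a splenectomy in week 6 and a count of 80,000/ul in week 8 meets the definition as written (timing and count invented for illustration).

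There is no control group to show how much of the response proportion comes from other interventions. Under the literal rule, such a patient can only raise the reported rate. If the question is left until results are in, classification would be decided case by case in an open-label study of 15 patients, with the counts already known.

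**Working it through.** **Inputs.** Treated patients: 15 (section 3.1). Response: one count above 50,000/ul within 12 weeks (8.3.1.1). Splenectomy: allowed throughout (5.4.2), raising counts in most patients (8.2). Frequency of splenectomy or rescue within 12 weeks: not given.

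**The plan's own figure.** Section 8.2.1 says that zero responders among 15 would make a true rate above 20% unlikely. The rule of three reproduces this: 3/15 = 20.0%. The exact one-sided 95% limit is 1 − 0.05^(1/15) = 18.1%, and the upper end of the exact two-sided 95% interval is 1 − 0.025^(1/15) = 21.8%. The figure stands. It does depend on the zero being a true zero: one misattributed patient turns 0/15 (0–21.8%) into 1/15 = 6.7% (0.2–31.9%).

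**Does the exit clause close the gap?** Two kinds of count remain unassigned.
- The count that shows effectiveness. Section 5.4.2 does not define effective. The natural evidence is a raised platelet count, which would then exist before participation ends.
- Counts after stopping. Section 6.1 asks for at least 4 weeks of counts at weekly to biweekly intervals, which is 4/2 = 2 to 4/1 = 4 counts (taking biweekly as every two weeks). If eltrombopag stops by the end of week 8, all of them fall inside the window (8 + 4 = 12).

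A lasting post-surgical rise would be picked up at any later draw: the scheduled month 2 and month 3 draws (taking month 3 as about week 12), or weekly draws if dose adjustment is still under way.

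**Effect of one misattributed patient.** Shift = 1/15 = 6.7 points. The reported rates below are assumptions. The middle row is the nearest whole number below the preliminary 5/8 = 62.5% in section 1.2 (0.625 × 15 = 9.4), which used a somewhat different definition of response. Intervals are exact (Clopper–Pearson) 95%.

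| Reported | After reclassifying one patient |
|---|---|
| 6/15 = 40.0% (16.3–67.7) | 5/15 = 33.3% (11.8–61.6) |
| 9/15 = 60.0% (32.3–83.7) | 8/15 = 53.3% (26.6–78.7) |
| 12/15 = 80.0% (51.9–95.7) | 11/15 = 73.3% (44.9–92.2) |

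At 9/15 the interval is 83.7 − 32.3 = 51.4 points wide, so one patient is small against sampling error. The difference is that this error has one direction and is not reflected in the interval.

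**The case against.** The best defence is that an effective splenectomy takes the patient off study, so a surgical rise was never meant to count. The 12-week window is justified by eltrombopag dose titration, and the third specific aim in 8.1 concerns daily eltrombopag. Section 6.3 shows that the counts after stopping are there to detect worsened thrombocytopenia. All of this supports an on-treatment intent. It remains intent: neither 8.3 nor 8.3.1.1 turns it into a scoring rule, and the count that triggers the exit is still unassigned.

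It is also fair that the study is exploratory, that section 8.2 stresses the sepsis risk of splenectomy (so early surgery may be uncommon, though that is inference), and that a listing of 15 patients would expose any affected case. These points limit the size of the problem. They do not tell the analyst how to classify the case.

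Four stronger readings are tempting, and the documents do not support them.
- *Rescue is as serious a route as splenectomy.* Section 5.4.1 bars other ITP therapy apart from stable oral steroids and IVIG. Section 8.2 calls IVIG and steroids ineffective in this disease and says a transfusion lasts only hours. Rescue is a minor route.
- *The plan would call one patient both a failure and a responder.* Section 6.4.3 says "thrombocytopenia that results in administration of rescue treatment does not qualify as an AE or SAE" and "hospital admissions that are attributable to such treatment failures or related therapy also do not qualify as AEs or SAEs". That wording governs adverse event reporting and is not an efficacy class. A patient may also respond first and need rescue later.
- *The dates needed to apply a rule are not collected.* Section 3.1 collects rescue use and requires a count at any change of concomitant medication, 6.4.5 tracks medications between visits, and the case report forms cited in section 7 are not available here. Missing date fields cannot be asserted.
- *The conflict among 5.4, 5.4.1 and 5.4.2 over permitted therapy is evidence for this point.* The conflict is real, but it is a separate matter.

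**Conclusion.** The point holds for splenectomy. The response rule, applied exactly as written, can credit a surgical platelet rise to eltrombopag, and the exit clause in 5.4.2 narrows that possibility without removing it. The size is 6.7 points per affected patient out of 15. This rests on all 15 being treated and in the denominator, and on the affected patient having no qualifying count before surgery.

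A reader might infer that the reported rate will be materially inflated. The documents do not support that: they give no frequency of splenectomy or rescue, and the bias is zero if no such case arises. The change should be made because a stated primary-endpoint rule would misclassify a foreseeable patient and the correction is cheap. Rescue and transfusion belong in the same rule, but would not justify it alone.

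**What to change.** Add to section 8.3.1.1:

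1. A platelet count taken after splenectomy does not qualify as a response. A qualifying count before splenectomy still does.
2. A count taken shortly after platelet transfusion or other rescue does not qualify. The length of that interval is fixed and justified before analysis. Counts before the rescue or after the interval can qualify.
3. A treated patient with no qualifying count is a non-responder. The denominator is all patients who received eltrombopag.
4. A sensitivity analysis repeats the primary proportion using all counts regardless of intervention.

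Confirm that the case report form dates splenectomy, rescue and transfusion precisely enough to be placed relative to each count.

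The cost is a few sentences and possibly a form check. The reported response rate may be slightly lower. A true responder whose only count above 50,000/ul follows splenectomy will be scored a non-responder, including a patient whose splenectomy was ineffective and who continued eltrombopag. The same can happen within the rescue interval. The sensitivity analysis shows how many patients are affected.

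Separately, 5.4, 5.4.1 and 5.4.2 must be reconciled on which other therapies are permitted and when. Section 5.4 extends its four-week bar to non-drug therapies while 5.4.2 places no time limit on splenectomy. Section 5.4.1 restricts other therapy for the whole study while 5.4.2 does so for the first four weeks.

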5.5. Treatment after the End of the Study

All ITP therapies including thrombopoietic agents can be used after the end of study.

5.6. Treatment of Investigational Product Overdose

Platelet counts will be followed carefully and treatment held for approximately one week if there is a significant drug overdose. Calcium-containing products could be used in the very unlikely event of a substantial overdose to inactivate the PROMACTA. Aspirin can also be given as needed.

5.7. Treatment Plan

	Adults and children > 30 kg	Children < 30 kg	Frequency
Urinalysis	10 mL	5 mL	One Time (at screen)
Admission Panel (includes ALT, AST, bilirubin)	2 mL	2 mL	Every two weeks for the first month; monthly for year 1; every 2 months for year 3; every three months for years 3 - 6
CBC with Platelet and Differential and Immature Platelet Fraction (IPF)	2 mL	2 mL	Every two weeks for the first month; monthly for year 1; every 2 months for year 3; every three months for years 3 - 6
PT/PTT, D-Dimers, Fibrinogen	5 mL	2.5 mL	One time (at screen)
PFA	5 mL	2.5 mL	One time (at month 2)
Single Platelet Flow Cytometry	10 mL	2 mL	3 times (at screen, at month 1-3 and at year 1-2)

NOTE: see schedule of events on page 25

Control subject blood draw	30 mL	10-20 mL	One time
WAS Non-treatment subject blood draw	30mL	10-20mL	One time

6. STUDY ASSESSMENTS AND PROCEDURES

6.1. Critical Baseline Assessments

Complete Blood Counts (CBCs)

CBCs, including platelet counts and peripheral blood smears, will be monitored prior to initiation, throughout, and following discontinuation of therapy with PROMACTA. Prior to the initiation of PROMACTA, the peripheral blood differential will be examined to establish the extent of red and white blood cell abnormalities. CBCs, including platelet counts and peripheral blood smears, will be obtained weekly during the dose adjustment phase of therapy with PROMACTA and then monthly following establishment of a stable dose of PROMACTA. CBCs, including platelet counts will be obtained weekly to biweekly for at least 4 weeks following discontinuation of PROMACTA.

Liver tests

Serum liver tests (ALT, AST, and bilirubin) will be monitored prior to initiation of PROMACTA, every 2 weeks during the dose adjustment phase and monthly following establishment of a stable dose. If bilirubin is elevated, fractionation will be performed. If abnormal levels are detected, the tests will be repeated within 3 to 5 days. If the abnormalities are confirmed, serum liver tests will be monitored weekly until the abnormality(ies) resolve, stabilize, or return to baseline levels. PROMACTA will be discontinued based on the stopping rules outlined in section 6.3.1

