Eltrombopag starting doses for children < 50kg will be scaled by body weight and the starting dose will be approximately 2 mg/kg once daily unless they are of East Asian origin in which case they will use approximately 1 mg/kg as their initial dose. This starting dose is based on the findings of GlaxoSmithKline's PETIT2 study: Eltrombopag for children with chronic immune thrombocytopenia (PETIT2): a randomised, multicentre, placebo-controlled trial.

This dosing schedule is based on those used in GlaxoSmithKline's 'PETIT' study: Eltrombopag in Pediatric patients with Thrombocytopenia from ITP.

For young children unable to swallow a tablet, eltrombopag powder for oral suspension (Eltrombopag PfOS) will be used. Each sachet contains eltrombopag equivalent to 20mg per gm of powder. Please see Appendix 3 for details and dose adjustment guidelines for subjects receiving the suspension formulation. Repeat assessment with the same testing will be performed at week 4. Dose adjustment will be based on the monthly monitoring of the platelet count.

The IPF will be measured at each visit with the CBC. Platelet count data will be collected throughout the study and used as part of the assessment of efficacy. Platelet count data will be collected as part of the CBC monthly during the first year of administration of study drug and at any dose change (eltrombopag or concomitant medication). If a subject continues on a stable dose during any stage of the study for greater than 4 weeks, a CBC (including platelet count) with differential will be performed no less frequently than every 4 weeks. Further information regarding reduction in use of concomitant medications for thrombocytopenia, use of rescue therapy, incidence and severity of bleeding and other symptoms associated with thrombocytopenia and infections will also be collected and summarized.

Platelet function will be assessed by whole blood flow cytometry as described by and in collaboration with [name] (see appendix for attached abstracts).

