6.3. Safety

This protocol is investigator initiated. The Principal Investigator is responsible for the study and will monitor the safety of the patients on the protocol.

The following safety will be reviewed by the Principal Investigator:

- Physical Exam
- Vital Signs
- Laboratory results (blood count, liver function tests, reticulocyte count, urine tests)
- SAE and AE events
- Bone marrow aspirations/biopsies (if relevant)

Adverse Events (AEs) will be graded according to Common Terminology Criteria for Adverse Events v4.03(CTCAE)The PI will determine the relationship of AEs to the test procedure/device/agent as not related, possibly related, probably related or definitely related, using standard criteria for clinical trials. Interim assessment of AEs will be conducted semi-annually by the data safety monitoring board.

Note: All serious adverse events will be followed until resolution of the events or definitive conclusion.

Hepatotoxicity

Administration of eltrombopag may cause hepatotoxicity. In the controlled clinical ITP studies, serum liver test abnormalities (predominantly Grade 2 or less in severity) were reported in 10% and 8% of the PROMACTA and placebo groups, respectively. Two patients (1%) treated with PROMACTA and two patients in the placebo group (3%) discontinued treatment due to hepatobiliary laboratory abnormalities. Seven of the patients treated with PROMACTA in the controlled studies with hepatobiliary laboratory abnormalities were re-exposed to PROMACTA in the extension study. Six of these patients again experienced liver test abnormalities (predominantly Grade 1) resulting in discontinuation of PROMACTA in one patient. In the extension study, one additional patient had PROMACTA discontinued due to liver test abnormalities (\leq Grade 3).

Serum ALT, AST, and bilirubin will be measured prior to initiation of PROMACTA, every 2 weeks during the dose adjustment phase and monthly following establishment of a stable dose. If bilirubin is elevated, perform fractionation. Evaluate abnormal serum liver tests with repeat testing within 3 to 5 days. If the abnormalities are confirmed, monitor serum liver tests weekly until the abnormality(ies) resolve, stabilize, or return to baseline levels. Discontinue PROMACTA if ALT levels increase to $\geq 3X$ the upper limit of normal (ULN) and are:

- Progressive, or
- Persistent for ≥ 4 weeks, or
- Accompanied by increased direct bilirubin, or

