- Accompanied by clinical symptoms of liver injury or evidence for hepatic decompensation.

Bone Marrow Reticulin Formation and Risk for Bone Marrow Fibrosis

Eltrombopag is a thrombopoietin (TPO) receptor agonist and TPO-receptor agonists may increase the risk for the development or progression of reticulin fiber deposition within the bone marrow.

In the ITP extension study, seven patients had reticulin fiber deposition reported in bone marrow biopsies, including two patients who also had collagen fiber deposition. The fiber deposition was not clearly associated with cytopenias and did not necessitate discontinuation of eltrombopag. However, clinical studies have not yet excluded a risk of bone marrow fibrosis with cytopenias and discontinuation of eltrombopag.

Prior to initiation of eltrombopag, examine the peripheral blood smear closely to establish a baseline level of cellular morphologic abnormalities. Following identification of a stable dose of eltrombopag, examine peripheral blood smears and CBCs monthly for new or worsening morphological abnormalities (e.g., teardrop and nucleated red blood cells, immature white blood cells) or cytopenia(s). If the patient develops new or worsening morphological abnormalities or cytopenia(s), discontinue treatment with eltrombopag and consider a bone marrow biopsy, including staining for fibrosis.

Worsened Thrombocytopenia After Cessation of Eltrombopag

Discontinuation of eltrombopag may result in thrombocytopenia of greater severity than was present prior to therapy with eltrombopag although this is only seen in a minority of patients who stop the drug. This worsened thrombocytopenia may increase the patient's risk of bleeding, particularly if

eltrombopag is discontinued while the patient is on anticoagulants or antiplatelet agents. In the controlled ITP clinical studies, transient decreases in platelet counts to levels lower than baseline were observed following discontinuation of treatment in 10% and 6% of the eltrombopag and placebo groups, respectively. Serious hemorrhagic events requiring the use of supportive ITP medications occurred in 3 severely thrombocytopenic patients within one month following the discontinuation of eltrombopag; none were reported among the placebo group.

Following discontinuation of eltrombopag, obtain weekly CBCs, including platelet counts for at least 4 weeks and consider alternative treatments for worsening thrombocytopenia, according to current treatment guidelines

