6.3.1. Liver chemistry stopping and follow-up criteria

Increased Liver Chemistries

Eltrombopag administration may cause hepatotoxicity. In the ITP controlled clinical studies, one patient experienced Grade 4 (NCI Common Terminology Criteria for Adverse Events [NCI CTCAE] toxicity scale) elevations in serum liver test values during therapy with eltrombopag, worsening of

underlying cardiopulmonary disease, and death. No patients in the placebo group experienced Grade 4 liver test abnormalities. Overall, serum liver test abnormalities (predominantly Grade 2 or less in severity) were reported in 10% and 8% of the eltrombopag and placebo groups, respectively. In the controlled studies, two patients (1%) treated with eltrombopag and two patients in the placebo group (3%) discontinued treatment due to hepatobiliary laboratory abnormalities. Seven of the patients treated with eltrombopag in the controlled studies with hepatobiliary laboratory abnormalities were re-exposed to eltrombopag in the ITP extension study. Six of these patients again experienced liver test abnormalities (predominantly Grade 1) resulting in discontinuation of PROMACTA in one patient. In the ITP extension study, one additional patient had eltrombopag discontinued due to liver test abnormalities (all \leq Grade 3).

Serum ALT, AST, and bilirubin should be measured prior to initiation of eltrombopag, every 2 weeks during the dose adjustment phase and monthly following establishment of a stable dose. If bilirubin is elevated, perform fractionation. Evaluate abnormal serum liver tests with repeat testing within 3 to 5 days. If the abnormalities are confirmed, monitor serum liver tests weekly until the abnormality(ies) resolve, stabilize, or return to baseline levels.

Once more than six patients are enrolled in the study: The study will be stopped if 33% of the patients develop any of the following labelled hepatotoxicity monitoring criteria for drug cessation.

Treatment with eltrombopag should be discontinued because of abnormal liver tests if any of the following 4 conditions apply:

- ALT levels \geq 3 times upper limit of normal (ULN) and bilirubin levels \geq 1.5 times ($>$ 35 % conjugated bilirubin) ULN,
- (2) ALT levels \geq 3 times ULN and appearance or worsening of hepatitis symptoms or rash,
- (3) ALT levels remain \geq 3 times ULN for $>$ 4 weeks, or
- (4) ALT levels are \geq 5 times ULN.

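### After year 1 the schedule of events and 5.7 give 22 blood draws to a patient on a stable dose, where the protocol's own rules require 60 liver tests and 60 to 65 blood counts

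*Combined protocol and SAP*

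**What the plan says.** Two sets of rules cover the same tests in patients who stay on eltrombopag.

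**The safety and design text**
- Section 6.1: blood counts with smears "will be obtained weekly during the dose adjustment phase of therapy with PROMACTA and then monthly following establishment of a stable dose".
- Section 3.1: for a patient "on a stable dose during any stage of the study for greater than 4 weeks", a blood count with differential is to be "performed no less frequently than every 4 weeks".
- Section 6.3, on hepatotoxicity: ALT, AST and bilirubin "every 2 weeks during the dose adjustment phase and monthly following establishment of a stable dose". Section 6.1 has the same rule, and 6.3.1 repeats it: these tests "should be measured prior to initiation of eltrombopag, every 2 weeks during the dose adjustment phase and monthly following establishment" of a stable dose.
- Section 6.3, on marrow reticulin: once the dose is stable, "examine peripheral blood smears and CBCs monthly for new or worsening morphological abnormalities".

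**The operational tables**
- Schedule of events, footnotes 5 and 6: blood is drawn two-monthly in the second year and three-monthly in years 3 to 6. Clinic visits are sparser still, every 4 and every 6 months.
- Section 5.7: the same pattern for the blood count and the admission panel, except that the two-monthly period is labelled year 3.

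No section says which text prevails.

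On dosing, 3.1 states: "Dose adjustment will be based on the monthly monitoring of the platelet count". Section 8.3.1.1 allows a change only every 2 weeks, and Appendix item 2 is headed as a weekly adjustment.

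**The concern.** A site that works from the schedule of events, as sites and local laboratories usually do, breaches the monitoring minimums that the same protocol sets for liver injury and marrow changes. About 80% of the 15 treated patients are expected to be children, and the schedule runs to month 72.

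The liver rules depend on timely testing. One discontinuation criterion in 4.4 and 6.3.1 is an ALT at or above 3 times the upper limit that persists for about 4 weeks. The study-level rule in 4.4.1, which stops the study when a third of patients meet the liver withdrawal criteria, can count only events that were detected. Section 9.2 plans no study monitoring, so nothing there would catch the gap.

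**Working it through.** The protocol states no total number of draws, so there is no figure to reproduce. The counts below are for one patient on a continuous stable dose from month 13 to month 72.

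**Schedule of events (footnotes 5 and 6) and 5.7, reading its year 3 label as year 2**
- Year 2: months 14, 16, 18, 20, 22, 24 = 6 draws.
- Years 3 to 6: months 27, 30, ..., 72 = (72 − 27)/3 + 1 = 16 draws.
- Total: 6 + 16 = 22.

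**Stated minimums**
- Monthly (liver tests in 6.1, 6.3, 6.3.1; counts with smear in 6.1, 6.3): 12 + 48 = 60.
- Every 4 weeks (blood counts only, 3.1): 5 × 365.25/28 = 65.2, so 65 (13 in year 2, 52 in years 3 to 6).

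| Test | Required | On schedule | Shortfall | Share provided |
|---|---|---|---|---|
| Liver tests | 60 | 22 | 38 | 22/60 = 37% |
| Blood counts, monthly rule | 60 | 22 | 38 | 37% |
| Blood counts, 4-week rule | 65 | 22 | 43 | 22/65 = 34% |

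**Longest gap between tests**
- Monthly: 5 × 365.25/60 = 30.4 days.
- Schedule, year 2: 2 × 30.4 = about 61 days.
- Schedule, years 3 to 6: 3 × 30.4 = about 91 days.

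An ALT elevation lasting 4 weeks (28 days) can begin and end unseen inside a 61-day or 91-day gap. Between monthly draws it would only just fit, and between 4-weekly draws it would not.

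**Do the two sets of rules truly conflict?** The safety rules are minimums, so 4-weekly draws also cover the schedule, but the reverse fails. The footnotes distinguish having blood drawn from being seen, so the draws themselves are thinned and not merely the visits.

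**Dose adjustment (minor).** The weekly, 2-weekly and monthly intervals cannot all hold. Section 6.1's weekly counts during titration are missing from 5.7 and the schedule, which give week 2, week 4 and then monthly. The length of the titration phase is not stated. If it lasted 12 weeks (an assumption), the weekly rule would give 12 post-dose counts and the schedule 4 (weeks 2 and 4, months 2 and 3).

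**The case against.** The best defence is that the taper is intended: less frequent draws in patients stable after a year spare children blood, and the safety text was simply never tied to year 1. That would be a coherent design, but the documents do not say it. Section 3.1 extends its minimum to any stage of the study, and no justification for thinning is offered. If the taper is meant, 3.1, 6.1, 6.3 and 6.3.1 need amending with a reason, so the text must change either way.

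A second defence is that abnormal liver tests trigger a repeat within 3 to 5 days and then weekly testing. That stands, but only once an abnormality has been found.

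Several stronger readings are tempting and are not supported:
- A reader might infer that 65 liver tests are required. The 4-week minimum in 3.1 covers blood counts only; the liver rule is monthly, so 60.
- A reader might put the wait for a smear abnormality at 2 to 3 months on the schedule. The schedule and 5.7 list no smear, so no smear interval follows from them.
- Section 6.2 might be counted among the conflicts. It is a timetable for collecting efficacy data, and sparser efficacy counts do not contradict denser safety monitoring.
- The year 3 label in 5.7 might be read as leaving year 2 unmonitored. It is an evident slip, since 6.2 and footnote 5 both say year 2.
- Sites might be said to have no means of knowing how to dose. Treatment starts at one centre and the principal investigator is responsible for patient safety, so this is a matter for harmonisation.
- The uneven number of early counts might be said to distort the 12-week response proportion. The documents give no within-patient variability from which to size such an effect, and the analysis is single-arm and descriptive.

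**Conclusion.** The conflict is real and follows from the text alone. For a patient on drug at a stable dose throughout months 13 to 72, the schedule and 5.7 provide 37% of the required liver tests and 34% to 37% of the required blood counts. The longest gap is two to three times the stated maximum of about a month. The counts are smaller for a patient who stops earlier, but the intervals still conflict. Nothing here shows that any patient was harmed or any event missed; the finding is that following the schedule breaches the protocol's own minimums. The plan should be corrected on this point. The dose-change intervals are a lesser inconsistency, and the primary endpoint is unaffected.

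**What to change.** **Main change.** In the schedule of events and 5.7, for patients on drug at a stable dose through month 72, require a blood count with smear at least every 4 weeks and ALT, AST and bilirubin at least monthly. Combine them in one draw, with a local laboratory allowed as in 3.1. Clinic visits stay as in footnotes 5 and 6. Wherever a two-monthly interval is kept in 5.7, label it year 2. Section 6.2 may stay as it is.

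**Cost per patient, at the 5.7 volumes of 2 mL per count and 2 mL per panel**
- Extra counts: up to 65 − 22 = 43, or 86 mL.
- Extra liver panels: 60 − 22 = 38, or 76 mL.
- Total: 86 + 76 = 162 mL over five years, all already required by the text. By year this is (7 + 6) × 2 = 26 mL in year 2 and (9 + 8) × 2 = 34 mL in each of years 3 to 6.

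Taking a panel with every 4-weekly count is simpler, and avoids the 8-week gap left when one of 13 yearly draws omits it. It adds 65 − 60 = 5 panels (10 mL), which would be a new requirement and should be declared as such. Bottles are already returned every 4 weeks (5.2), which gives a natural contact point.

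**Minor change.** Choose one dose-change interval, state it in 3.1, 8.3.1.1 and Appendix item 2, and put the matching titration counts into 5.7 and the schedule. Leave the primary endpoint in 8.3.1.1 unchanged.
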